5.0 STUDY PROCEDURES

5.1 Enrollment Procedures

We will enroll a total of 750 participants. Of these participants, 300 will be HIV-negative and 450 will be HIV-positive. After participants are consented, participants will complete a baseline CASI survey and then will be randomized into the Tailored Information-Only Control (Attention Control), Researcher-Created HMP Network (Intervention Arm 1), or HMP with Peer-Referral Network (Intervention Arm 2). Intervention Arm 2 will only have 150 HIV-positive participants randomized to it, as the remaining participants will be peers who are referred by their peers and enroll if eligible. Upon enrollment, all participants will be provided a link to access the HMP app through the Apple App Store or the Google Play Store for Android. Once downloaded, participants will create their app account by entering their email address, creating a username, password, and PIN, entering their mailing address, opting in or out of notifications, and selecting an avatar.

Those randomized in the Tailored Information-Only Control (Attention Control) will be given a streamlined version of the app. They will have access to the Care Locator and Knowledge Center articles and be able to message the Care Navigator. HIV-negative and sero-unknown participants will be able to request HIV home test kits. HIV-positive participants will be sent HemaSpot devices at Baseline, 6 months, and 12 months. They will not have access to the interactive forums, activities, or the Ask and Expert feature.

Those randomized in the Researcher-Created HMP Network (Intervention Arm 1) will have access to the full HMP app, including access to the Arm 1 Forum in which participants will be able to create threads and comment on any threads in the forum, whether moderator- or usergenerated.

Those randomized to the Peer-Referral Network (Intervention Arm 2) will have access to the full HMP app, including access to the Arm 2 Forum in which participants will be able to create threads and comment on any threads in the forum, whether moderator- or user-generated. The only difference between this version and the Intervention Arm 1, is that two thirds of the users (300) that comprise this group are added by peer referral by the 150 participants who were randomized into this arm.

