- 7. Risk of offensive/upsetting language or cyber bullying: We will strive to create a safe and comfortable app environment for all study participants. However, it is possible that participants in the two treatment arms may experience emotional discomfort or upset due to things other participants post through the intervention app' forums. The forums are monitored by study staff, however we do not require posts to be pre-approved by study staff before they go live in the app. We will include "community guidelines" as part of the intervention app's on-boarding process. This information is also included within the app as its own screen and reminders will be provided at all study follow-up assessments. These guidelines were developed and used successfully for participants in the original HMP intervention. Indeed, only one post out of 1497 posts met the criteria for a guideline violation. Thus, we believe the likelihood and seriousness of this risk is minimal. During the adaptation and final development of HMP Stigma we will ask Youth Advisory Board members to review and help update the guidelines to ensure they are comprehensive given the regular evolution of online environments and social media tools. The guidelines will continue to include language around non-discrimination, non-offensive language, openness and confidentiality. As in the original HMP intervention, during the study RCT, study staff will monitor all participant posts during business hours with posts made outside of business hours reviewed in the morning of the next business day. If a participant posts something that could be considered in breach of the guidelines, study staff will remove the post, contact the participant to notify them, explain why the post was removed, provide them with a copy of the guidelines to review again and post a note from the study team to the forum reminding all participants to review and adhere to the guidelines. If a participant accumulates three violations of this nature, they will be immediately discontinued from the study. Any threat of harm to others would be grounds for considering immediate study

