stop. The reason we choose to allow more than one violation is that one of the key mechanisms of change for the intervention is for participants to become more aware of the conscious and unconscious stigmatizing beliefs they hold – as well as to challenge these stigmatizing views in others. Thus, we think that these violations can provide a learning opportunity for all parties if handled intentionally. The grounds for discontinuation will be made clear during the informed consent process and will be stated explicitly online within the app use guidelines. Study protocol will include a Standard Operating Procedures manual for staff that will include directions for referral and follow-up in the event that a participant expresses emotional discomfort, distress, threats to self or others, or suicidality.

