8.4 Criteria for Premature Study Discontinuation

The principal investigator has the authority to withdraw any participant at any time if in their opinion it would be in the best interest of the participant. The participant will be informed of this withdrawal and explained the rationale. Withdrawal will be documented in the study tracking system. Subjects will be prematurely discontinued from the study if any of the following occurs:

- The subject withdraws consent/assent;
- The study is cancelled by the NIMHD;
- The study is cancelled for other administrative reasons;
- The subject becomes incarcerated or placed in detention during the study; or
- Death of the subject.

Participants may end their participation in the study at any time. No further data collection will occur from the date the decision is made to permanently discontinue the subject from the study. Participants who experience distress during the study will be provided a list of community referrals via phone or email. Any adverse events will be immediately reported to the U Penn IRB and the respective sites' IRBs if applicable. The *Study Stop and Adverse Event Forms* will be completed at this time.

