10.2 Power Estimates

The primary outcome for the proposed trial is stratified by HIV status and defined as *successful* engagement in care. For HIV-positive participants at baseline, we define successful engagement in HIV care as consistent VS across the 12-month trial (per IOM guidelines²¹⁸). For HIV-negative

or sero-unknown at baseline, we define successful engagement in care as participation in routine HIV testing (2 HIV tests with at least 3 months apart from one another, per CDC guidelines²¹⁹). We define power as correctly identifying the difference in the proportions of YBLMT with serospecific engagement in HIV care within 12 months of each intervention arm (2 arms: HMP Stigma with researcher-created network, HMP Stigma with peer-referred network) to the control arm (Information Control), thus powering for 3 independent hypothesis tests. Our sample size calculations are based on pair-wise HIV-stratified comparisons of the 3 groups in terms of proportion of successful engagement using a two-sided significance level of 0.05 altered by the number of comparisons using a Bonferroni adjustment (significance level is 0.017 for 3 comparisons). To have 80% power to detect a minimum effect size (OR=1.9) of successful engagement in care between the 3-arm trial, we will require at least 450 HIV-negative and 450 HIV-positive participants to detect a 17% difference in successful engagement in. In the event of a 20% loss to follow-up, we will have sufficient power to detect an OR=2.1 (18% difference) at alpha=.017. Participants may continue the study even if they miss an assessment intermittently. We will compare those who completed different follow-up interviews with those who did not on key baseline predictors to check for possible sampling bias. Our analysis will use ITT as appropriate.

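### Three forum violations end all study follow-up, a loss that can occur only in the two intervention arms; the expected number is small, but the loss is avoidable

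*Combined protocol and SAP*

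**What the plan says.** Section 8.3, item 7, has staff remove a post that may breach the community guidelines and notify its author. It then states: "If a participant accumulates three violations of this nature, they will be immediately discontinued from the study". The removal is from the study, not from the forum or the app. Section 8.4 gives the consequence: "No further data collection will occur from the date the decision is made to permanently discontinue the subject from the study".

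Only the two HMP arms have forums. Section 5.1 says of control participants: "They will not have access to the interactive forums, activities, or the Ask and Expert feature". Section 8.3 locates the risk in the same way: "it is possible that participants in the two treatment arms may experience emotional discomfort or upset due to things other participants post".

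The grounds listed in 8.4 are withdrawal of consent or assent, cancellation by the funder, cancellation for other administrative reasons, incarceration or detention, and death. The three-violation ground is not among them. I found no section that keeps a removed participant in outcome follow-up.

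On analysis, 10.2 says "Our analysis will use ITT as appropriate". Section 10.4 begins with cases that have the primary endpoint and follows with imputation whose form is left open.

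**The concern.** A rule that can stop follow-up in the intervention arms and never in control works against comparing the groups as randomised. Arm 1 and the 150 randomised members of Arm 2 are compared with control on engagement in care and, secondarily, on stigma (10.3.1). Follow-up lost through this rule has no counterpart in control.

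The rule may also select on something close to a measured outcome. To explain why more than one violation is allowed, 8.3 appeals to how the app is meant to work: "key mechanisms of change for the intervention is for participants to become more aware of the conscious and unconscious stigmatizing beliefs they hold". People removed for repeated violations could therefore differ on the stigma scales.

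The loss is unnecessary. Surveys go out by email and text as well as through the app (7.3.2), HemaSpot kits go by mail (5.4.2), and participants who miss assessments may stay in the study (8.1). Breaking a forum rule prevents none of this.

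**Working it through.** **1. Who is exposed.** Arm 1 has 150 HIV-positive and 150 HIV-negative or status-unknown members (3.2), so 300. Arm 2 has 150 randomised members and about 300 referred peers (5.1), so 450. Forum users: 300 + 450 = 750, of whom 300 + 150 = 450 are randomised. Control: 0. (This 750 is not the 750 in 5.1, which counts researcher-recruited participants including control.)

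**2. The plan's own rate.** Section 8.3 reports that in the earlier trial "only one post out of 1497 posts met the criteria for a guideline violation". 1/1,497 = 0.067% of posts, with exact 95% limits of 0.002% and 0.37%.

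**3. Posting volume.** The plan gives none for this trial. The earlier trial had 474 participants (1.1): 1,497/474 = 3.2 posts each, or 1,497/237 = 6.3 if half had forum access (assumed). The 20 and 100 below are assumptions for heavier use.

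**4. Expected removals among 750 users.** Violations = total posts / 1,497. If violations cluster as tightly as possible, the most people who can reach three is violations / 3, rounded down. If violations are independent, the expected number is 750 × P(at least 3), binomial.

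| Posts each | Total posts | Violations | Most removed (full clustering) | Independent, at 1/1,497 | Independent, at 0.37% |
|---|---|---|---|---|---|
| 3.2 | 2,369 | 1.6 | 0 | < 0.001 | < 0.001 |
| 6.3 | 4,737 | 3.2 | 1 | < 0.001 | < 0.001 |
| 20 | 15,000 | 10.0 | 3 | 0.0003 | 0.04 |
| 100 | 75,000 | 50.1 | 16 | 0.03 | 4.8 |

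Up to 20 posts each, at the earlier rate, the answer is 0 to 3 of 750 (3/750 = 0.4%). Going beyond that takes much heavier posting or a higher violation rate.

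**5. Effect on the primary endpoint.** Take one arm of one HIV stratum, n = 150, with an assumed 50% success rate (75 successes) and k people removed, all in that arm.

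- Complete cases, every removed person a would-be failure: 75/(150 − k) − 0.50. For k = 1, 3, 5 this is +0.3, +1.0 and +1.7 percentage points.
- Missing counted as failure (which 10.4 neither states nor rules out), every removed person a would-be success: −k/150. For k = 1, 3, 5 this is −0.7, −2.0 and −3.3 points.

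Both are worst cases. The target difference in 10.2 is 17 points, and its 20% loss allowance is 0.20 × 150 = 30 people per arm and stratum. The sign changes with the missing-data rule. Some endpoints are also settled before removal: an HIV-positive participant already found unsuppressed, or an HIV-negative participant with two tests at least 3 months apart.

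**6. Effect on a stigma score.** If a fraction f is dropped and scores 1 SD worse than those who remain (assumed), the observed mean improves by f × 1 SD. Three of 750 gives 0.004 SD. If all three were in Arm 1, 3/300 gives 0.01 SD.

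**The case against.** The strongest reply is that this hardly matters. The documents' own rate implies close to zero removals, 8.3 gives a deliberate reason for the rule and promises to disclose it at consent, and 8.4 does not call its list exhaustive. The point about size stands. The omission from 8.4 is a cross-reference gap, though one that needs closing.

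Three stronger readings are tempting, and the documents do not support them.

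- A reader might infer that a few percent of an arm could be lost. Removing 3% of Arm 1 means 9 people and 27 violations. At the earlier rate that takes 27 × 1,497 = 40,419 posts, about 135 per Arm 1 member, even with perfect clustering.
- A reader might infer that the bias must favour the intervention. No section links forum violations to viral suppression or HIV testing. The guidelines also cover openness and confidentiality, so a violation need not be stigmatising. For the stigma outcomes the link is plausible from 8.3 but not measured, and steps 5 and 6 show that direction depends on who is removed and how 10.4 is applied.
- A reader might extend the argument to withdrawal by the investigator. Section 8.4 says: "The principal investigator has the authority to withdraw any participant at any time if in their opinion it would be in the best interest". That power applies in every arm, and 8.3 (item 2) names completing the surveys as a possible source of distress, so ending them may be the purpose of the withdrawal.

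A practical objection also has force. HIV self-tests are ordered in the app, result photos are uploaded there, and a replacement HemaSpot kit depends on app records that the instructional video was viewed (5.4.2, 5.4.3). Removing someone from the whole app could itself affect the testing endpoint. The remedy should therefore reach the forum only.

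**Conclusion.** The point holds as a structural flaw of small expected size. A stated rule, and not merely a missing detail, ends follow-up of randomised participants for a reason that cannot occur in control, and 8.4 does not list that reason. The estimate of about 0 to 3 of 750 forum users assumes the earlier trial's rate and no more than 20 posts each. The rate could be higher here: 3.3.1 reshapes the forums to elicit sharing about stigma, and 4.1 admits ages 15 to 17, against 18 to 30 in the earlier trial (1.1).

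For the primary endpoint the established harm is avoidable, arm-specific missing data, with no demonstrated bias. For the secondary stigma outcomes bias is plausible, of uncertain direction, and about 0.01 SD or less under the assumptions above. The case for change rests on how cheaply the loss can be avoided. It does not rest on any threat to the trial's conclusions.

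**What to change.** In 8.3, 8.4 and the consent form, keep the three-violation rule as written and change only its consequence:

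- The participant loses forum access and remains in the study.
- In-app test-kit ordering and photo upload stay available, so the HIV-testing endpoint is not affected. The control app already offers kit ordering without forums.
- Surveys continue by email or SMS, and HemaSpot kits by mail, on the planned schedule.
- The participant is analysed in the assigned arm.
- The grounds listed in 8.4 are reconciled with 8.3.

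This leaves the separate provision in 8.3 on threats of harm to others, and withdrawal by the investigator, as they are. Follow-up lost because of the violation rule would then be zero in every arm by design. The cost is the rewording, a check that forum access can be switched off by itself for a single account, and incentives, kits and staff contact for the few people affected.

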8.4 Criteria for Premature Study Discontinuation

The principal investigator has the authority to withdraw any participant at any time if in their opinion it would be in the best interest of the participant. The participant will be informed of this withdrawal and explained the rationale. Withdrawal will be documented in the study tracking system. Subjects will be prematurely discontinued from the study if any of the following occurs:

- The subject withdraws consent/assent;
- The study is cancelled by the NIMHD;
- The study is cancelled for other administrative reasons;
- The subject becomes incarcerated or placed in detention during the study; or
- Death of the subject.

Participants may end their participation in the study at any time. No further data collection will occur from the date the decision is made to permanently discontinue the subject from the study. Participants who experience distress during the study will be provided a list of community referrals via phone or email. Any adverse events will be immediately reported to the U Penn IRB and the respective sites' IRBs if applicable. The *Study Stop and Adverse Event Forms* will be completed at this time.

9.0 MONITORING UNTOWARD EFFECTS ASSOCIATED WITH OR RESULTING FROM STUDY

Site staff must first follow their own IRB's procedure for reporting and managing untoward effects.

There are three types of untoward effects to be identified: (1) those related to the participant, (2) those related to the study staff, and (3) those related to the neighborhood/community.

First, the study will catalogue any untoward effect related to the participant. Reporting is required for occurrences including social harms, psychological distress and serious life-threatening events such as suicide attempts. These may be immediately apparent to the study staff, such as the participant's emotional upset requiring referral for counseling; or they may be delayed and reported later to study staff, such as physical harm to an individual for having participated in the study. Study staff will notify the team of these untoward effects by email. Study staff will be briefed during the training on the scope of possible untoward effects and instructed to report events.

Second, study staff may encounter untoward events during sessions that personally affect them. Training and guidance will seek to minimize this risk. Nonetheless, an assessment of the cost of

conducting this study must include cataloguing these events as well. The protocol chairs should be notified of these events so that they may be immediately addressed, evaluated, and guidance modified or expanded to minimize similar risk to other staff.

Third, a critically important area any community-based study intends to evaluate is the impact, including untoward effects, of the project on the community. This will be done informally for this protocol with untoward events being reported to the protocol team.

10.0 STATISTICAL/ANALYTIC CONSIDERATIONS

10.1 Introduction

10.1.1 Paradata Metrics

We will measure temporal engagement by examining users' visits to the app and time spent on app using HMP's paradata timestamps at each login and logout. The paradata will also include information allowing us to link engagement for users who create, like, read, or otherwise interact with content in the app. We will also calculate scores for each participant based on their levels of "active" (posting, commenting) and "passive" (reading) engagement. Active engagement scores will be calculated by assigning one point for each time a participant posted or commented on app content. Passive engagement scores will be calculated using the paradata database to assign a participant one point for each time they read content. Aggregate engagement scores for each participant will be included as indicators and latent factors, as appropriate, in our analyses. This strategy will allow us to examine how different forms of engagement (e.g., temporal engagement, active engagement, passive engagement) influence our study outcomes.

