2.0 STUDY OBJECTIVES

2.1 Primary Objective:

The primary outcome is successful engagement in care, defined as consistent viral suppression for HIV-positive participants and routine testing for HIV-negative participants.

2.2 Secondary Objective:

A secondary objective is whether user engagement, as measured by both quantitative and qualitative paradata, mediates the intervention effects observed in stigma and HIV care outcomes.

An additional secondary outcome is how changes in intersectional stigma and improvements across the HIV care continuum vary between the researcher-driven vs. peer-referred social network intervention conditions.

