3.3.2 Intervention and control arms

Participants in all arms will have access to a Care Navigator through the intervention or control app. The Care Navigator will utilize existing online databases of resources (e.g. AIDSVu.org Locators, CDC's GetTested.cdc.gov locators, POZ.com's Service directory) to connect participants to trusted HIV testing and care services in their communities as needed. The Care Navigator will also monitor the Forums to identify additional HIV knowledge needs and manage the Ask an Expert provider Q&A to triage medical questions to one of two board-certified HIV care providers. During all study years the Care Navigator will work closely with the YAB to elicit service-related needs and concerns among YBLMT that can be integrated into HMP Stigma.

Control Arm: The HMP Stigma Information-Only Control Arm will feature a streamlined version of the app that provides curated information and other content for YBLMT. This content will follow the design of HMP Original where control arm participants had access to HIV-related Knowledge Center articles of the main intervention without access to the engagement features such as the interactive forums or doctor Q&A. HIV-negative and sero-unknown participants will also be able to request HIV home test kits. Our choice of control arm balances equipoise with research study design; in HMP Original, control arm participants also experienced a statistically significant intervention benefit.⁴⁷ We have taken this effect into account in our sample size calculations.

HMP Stigma: We have used the Stigma Framework¹²⁸ alongside our findings from HMP Original to guide the design of our proposed intervention features and content (Table 1) and study measures (Table 2). Eligible, enrolled participants who are randomized to intervention Arms 1 (researcher-created network) and 2 (peer-referred networks) will have access to all the features of HMP Stigma. These features include forums where users can start or participate in threads, a knowledge center filled with short articles on a range of topics that can be added and commented on, a provider platform where health questions can be submitted to be answered by a health care provider, a user profile where users can personalize and update their information, and finally, an ordering platform where users can order and track testing kits.

Table 1: HMP Stigma Core Intervention Components and Scientific Rationale						

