8.2 Compensation

We will collect behavioral assessments at baseline (BL), 3, 6, 9, and 12 months. Participants will earn up to \$340 for completing the 5 behavioral surveys. Amounts per assessment vary based on estimated survey duration (BL-\$50, 3mo-\$35; 6mo-\$50, 9mo-\$35, 12mo-\$60). Any participant who completes four of the five behavioral assessments will receive a \$50 bonus incentive at the end of the study. We will collect HemaSpot blood samples for HIV Viral Load from HIV-positive participants at BL, 6, and 12 months. For equipoise, we will also offer free in-home HIV testing kits for all HIV-negative and HIV-unknown YBLMT. Participants will receive \$20 for using the prepaid shipping packaging to return HemaSpot device to the lab for processing (if HIV-positive) or for uploading a photograph of the HIV test stick that shows their in-home HIV test result (if HIV-negative or sero-unknown). HIV-positive participants are eligible for the incentive if they return their HemaSpot device to the lab within 45 days of receiving it. If an HIV-positive participant submits a HemaSpot device with a sample that cannot be processed and we confirm in the app's paradata that they have viewed the instructional video, they will be offered a chance to redo the

test kit. If they complete a replacement test and mail it to the lab, they will receive another \$20 incentive, regardless of the specimen's viability.

Participants who report seroconverting during the study or who upload a positive HIV test stick photo, after receiving confirmatory testing will be eligible to begin receiving HemaSpot device testing and incentives following the study's planned schedule. We will use paradata metrics to characterize users' engagement across the three arms.

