10.1.2 Mixed-Methods Paradata Forum Coding

Expanding on the procedures developed and successfully employed in our R21,49 we will conduct a mixed-methods analysis of user-contributed content to the forums. All content and associated paradata of each user post will be captured by HMP's backend database. We will use Dedoose cloud-based qualitative data analysis program to catalogue and code all instances of stigma-related content and characterize their potential contributions to HIV risk and care behaviors. First, two coders will independently identify all posts that contain stigma-relevant content. Next, they will conduct a content analysis to categorize the nature of the coded stigma content as enacted, community, anticipated, internalized, or challenged stigma. Coding discrepancies will be reviewed and resolved by a third analyst. Ongoing analysis progress will be discussed during biweekly YAB meetings and feedback sought on YAB members' interpretations of participant forum conversations and emergent themes. The final coded dataset will be used for qualitative analyses and publications, as well as to create user-specific variables representing their engagement with each type of stigma-related domain. These data will be used to examine how engagement with stigma content is associated with changes across HIV outcomes (HIV testing, VS) directly and through proposed mediators (e.g., social support and isolation, substance use, depression). We successfully used this methodology in our R21 analysis and have established analytic protocols to carry out these procedures.49-51

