10.3.2.1 Quantitative Analyses

Building our theoretical framework, we will use structural equation modeling (SEM) to test whether engagement with stigma content predicts changes in stigma-related outcomes over time (e.g., decreases in anticipated HIV stigma), and changes in HIV care outcomes over time (e.g., repeat HIV testing; consistent VS). In these HIV-stratified analyses, we will use latent class analysis to characterize users' engagement in the app. We will estimate the independent contributions of passive and active engagement on both stigma and HIV outcomes, as well as how cumulative engagement in stigma-related discussions influences these outcomes. Key sociodemographic predictors will be included as covariates (e.g., age, time since diagnosis). We will also examine the contribution of specific mediators (e.g., social support) in these models by decomposing the total effects into direct and indirect effects. In exploratory analyses, we will use multigroup SEM analyses to test whether these proposed models differ based on latent classes of users (e.g., active forum contributors vs. lurkers; low, moderate, high engagement). Multigroup analyses allow us to compare the strength and direction of the effect sizes in our models and their overall fit across these engagement groups. Ideal models will have values of .90 or higher among fit indices and values of .06 or lower for RMSEA as acceptable indicators.85 The proposed study has sufficient power to carry out these subsample analyses in our model identification and model testing stages. MacCallum et al.²²⁰ show that power of .80 is achievable with alpha=.05 and 30 degrees of freedom in cross-sectional analyses with a sample of 366 for a close model fit (for df=100 the minimum sample size is 178). Thus, we have ample power for these SEM analyses, even when dividing the sample by HIV status or engagement profile.

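### Two Aim 2 engagement scores are zero, or in effect zero, in the control arm, so without adjustment for shared causes the mediation analysis can credit engagement when the app does nothing

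*Combined protocol and SAP*

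**What the plan says.** Section 2.2 asks whether engagement "mediates the intervention effects observed in stigma and HIV care outcomes", and section 10.3.2 repeats this as Specific Aim 2, worded as exploration.

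The scores are defined in section 10.1:
- **Active:** "Active engagement scores will be calculated by assigning one point for each time a participant posted or commented on app content".
- **Passive:** the paradata database is used to "assign a participant one point for each time they read content".
- **Temporal:** visits and time on the app.
- **Stigma content:** "we will conduct a mixed-methods analysis of user-contributed content to the forums" (10.1.2). The coded data are then used to "create user-specific variables representing their engagement with each type of stigma-related domain".

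Under section 3.3.2 the control app offers Knowledge Center articles "without access to the engagement features such as the interactive forums or doctor Q&A". Section 5.1 also withholds forums, activities and the expert feature from control. Adding to and commenting on articles is described in 3.3.2 among the features of Arms 1 and 2.

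The Aim 2 model in 10.3.2.1 is an HIV-stratified SEM to "test whether engagement with stigma content predicts changes in stigma-related outcomes over time", and likewise changes in HIV care outcomes. Total effects are split into direct and indirect effects, with social support given as an example mediator. Age and time since diagnosis are the example covariates. Section 8.2 adds: "We will use paradata metrics to characterize users' engagement across the three arms".

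**The concern.** A claim that engagement mediates the effect of intervention versus control needs two paths: arm to engagement, and engagement to outcome. If the score is zero for every control, the first path is non-zero as soon as anyone in Arms 1 or 2 posts, whether or not the app works. The second path is then estimated only by comparing keen with less keen users in the app arms, and nobody was randomised to be keen.

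Motivated participants may both post more and test or adhere more. The decomposition then gives a positive indirect effect and an offsetting negative direct effect, even when the total effect is nil.

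The protocol's own background makes this plausible. In HMP Original, use of the social features was associated with better HIV care outcomes, while viral suppression rose in both arms (section 1.1) and control participants also benefited (section 3.3.2). At stake is a published claim about mechanism, and a decision on which app features to keep.

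**Working it through.** **1. Which scores can vary in control**

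| Score | Source | Control arm |
|---|---|---|
| Stigma content | coded forum posts (10.1.2) | zero by design: no forum (3.3.2, 5.1) |
| Active | posts and comments (10.1.1) | in effect zero; commenting on articles is neither offered to control nor expressly barred |
| Passive | items read (10.1.1) | can vary; articles only, whereas app arms also read forum posts |
| Temporal | visits, time on app (10.1.1) | can vary |

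**2. The plan's own figure.** Section 10.3.2.1 cites minimum samples of 366 (df = 30) and 178 (df = 100) for 80% power at alpha 0.05. The usual RMSEA calculation uses a noncentral chi-square with noncentrality (N - 1) x df x RMSEA². The documents do not give the RMSEA pair. Assuming null 0.05 against alternative 0.01 gives 367 and 178, which matches. Null 0.05 against 0.08 gives 314 and 132. These figures concern overall model fit and say nothing about power for, or bias in, an indirect effect.

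**3. Algebra.** Let A be arm (0 or 1), M the score and Y the outcome.
- Path a: M on A. With M = 0 in control, a is simply the mean score in the app arms.
- Path b: the M slope in the regression of Y on A and M. With M constant in control, b comes entirely from the app arms.
- Indirect effect = a x b. Direct effect = total - a x b. If the total is 0 and b > 0 through a shared cause, the direct effect must be negative.

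**4. Simulation, continuous outcome.** App without effect on outcome; 150 control and 300 app participants (150 per arm from section 3.2, Arms 1 and 2 pooled: 150 + 150 = 300). An assumed trait correlates r with both engagement and outcome. Least squares, Sobel test of a x b > 0 against 1.96, nominal one-direction rate 2.5%.

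| r (assumed) | Score zero in control | Shared metric that the app raises by 0.5 SD (assumed) |
|---|---|---|
| 0.2 | 9% | 10% |
| 0.3 | 32% | 39% |
| 0.4 | 78% | 90% |
| 0.5 | 99% | 99.7% |

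Adjusting for the trait brings the rate to about 2.5-3%.

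**5. Simulation, binary outcome.** Skewed count score (mean 3, analysed as log(1 + count)), zero in control; outcome about 50%; app without effect. An unmeasured trait acts with log-rate slope g on the score and log-odds slope b on the outcome (here b is the trait's slope, not path b). Robust standard errors, Sobel test, two-sided nominal 5%, 1000 runs per setting.

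| g = b (assumed) | 150 vs 150 | 150 vs 300 |
|---|---|---|
| 0 | 4.7% | 3.9% |
| 0.3 | 7.6% | 9.4% |
| 0.5 | 17.4% | 33.4% |
| 0.7 | 46.4% | 73.6% |
| 1.0 | 86.3% | 98.8% |

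- At g = b = 0.5 and 150 vs 150, the mean indirect effect was +0.050 and the direct effect -0.048, a total of 0.050 - 0.048 = 0.002.
- With the trait measured and adjusted, the rate was 5.0-6.2% (150 vs 150) and 5.5-6.2% (150 vs 300).
- With a metric that varies in all arms and that the app does not move, it was 0.2-2.7% and 0.3-3.8%.

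**6. Can a zero-in-control score recover real mediation?** With a true effect of engagement (log-odds 0.5 per log unit), no confounding and 150 vs 150, the indirect effect was 0.123 of a total 0.125. With confounding of 0.5 it was 0.100 of 0.108 when adjusted. Unadjusted, it was 0.150 of 0.108, with a direct effect of -0.041.

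**The case against.** **A reader might infer that scores fixed at zero in control can never show mediation.** The documents and the check do not support that. Step 6 recovers a real indirect effect when shared causes are absent or adjusted for, and without a shared cause the error rate stays near nominal. Unmeasured confounding of engagement and outcome is a general limit of mediation analysis. This objection stands in full.

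**A reader might also infer that moving to metrics available in every arm cures the problem.** It does not: step 4 shows the same error if the app raises the metric. Such metrics are also already planned (visits and time in 10.1.1; articles read in Table 1).

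**The plan may not intend an all-arm model.** Section 10.3.2.1 never says control enters the SEM and writes no arm-to-engagement path. It speaks of engagement predicting change, and it compares forum contributors with lurkers, who exist only in Arms 1 and 2. The 8.2 sentence is descriptive. This stands as a reading, but an app-arm-only SEM is a dose-response analysis and does not answer the mediation question in 2.2 and 10.3.2. Either reading needs a correction.

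**Covariates may be fuller than the examples.** Section 5.4.4 refers to a Table 2 of potential covariates that is not in the text available here, and modelling change brings in baseline to some degree. So it cannot be said that the plan omits baseline adjustment, only that 10.3.2.1 does not commit to it.

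**Aim 2 is secondary and exploratory.** True, and that limits the severity.

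**Conclusion.** The concern holds in this form. The stigma-content score is zero by design in control and the active score is in effect zero. An intervention-versus-control decomposition using them therefore has a guaranteed first path and a second path that rests on non-randomised differences within Arms 1 and 2. As 10.3.2.1 is written, it can report mediation by an app that does nothing. The cause is unadjusted confounding between engagement and outcome; the zeros remove the safeguard that an ineffective app would leave engagement unchanged.

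The size depends on confounding strength, for which the documents give no figure. It runs from little inflation (about 8-9% against 5%, binary outcome, g = b = 0.3) to near certainty under strong confounding. The highest rates should not be read as expected. That Aim 2 will in fact credit the forums with benefit is conjecture. The temporal and passive scores are not zero in control and fall outside the first part of the point.

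This should be corrected before analysis, but it does not touch the primary comparison.

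**What to change.** In section 10.3.2.1:
1. State which arms enter the SEM and write out the arm-to-engagement path, if there is one.
2. Adjust every engagement-outcome path for the baseline value of the outcome (testing history, viral load, adherence), baseline stigma and other baseline predictors of engagement already collected. Add a sensitivity analysis for unmeasured confounding.
3. Analyse forum, active and stigma-content engagement within Arms 1 and 2 only. Report it as an association with outcome, and state that it is not evidence that the intervention-versus-control effect is mediated.
4. If an intervention-versus-control mediation model is kept, use metrics that every arm can generate (log-ins, time on app, articles read), with the same adjustment and the no-unmeasured-confounding assumption stated. Shared metrics without the adjustment are not enough.

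The cost is SAP wording and some analysis time. The study schema already schedules a baseline survey for all participants and baseline viral load for HIV-positive participants, so no new visit is needed. The downside is that the forum-engagement claim becomes associational and excludes control.
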